RESEARCH PROTOCOL: PART 1

Project Summary

Rationale: Dietary modification and reduction of daily fluid intake constitute the conventional therapeutic measures for toddlers' diarrhea. Compliance with these measures can be challenging for the child. Using pharmacotherapy may be an attractive option given the published report showing that proton-pump inhibitors or H2-receptor blockers can effectively control the frequent bowel motion and post-prandial urgency associated with this functional bowel disorder.

Objective: To determine the effectiveness of a short course of daily oral ranitidine in the treatment of toddlers' diarrhea

Methods: A parallel-group randomized controlled trial (RCT) in which each participant is to be randomly assigned to three groups after meeting the eligibility criteria. The three groups of participants will consist of a group to be given daily oral ranitidine (3mg/kg) for 10 days (oral ranitidine group- ORG), the group that will receive probiotics for 10 days (PBG), and the control group that will be given a placebo (vitamin C- 50mg daily) for the same duration.

Populations: 40 participants who met the following eligibility criteria-(1) Age range of 1-3 years (2) Duration of diarrhea lasting 3 weeks or more (3) Historical evidence of the characteristic stooling pattern (3) Absence of pyrexia and signs of dehydration (4) Normal anthropometry and (5) Normal findings on stool analysis, microscopy, and culture.

Time frame: Three years

Expected outcomes: Stool frequency and consistency recorded on the 5th and 10th day, and follow-up documentation 30 days after the end of interventions. Normalization of stool frequency and consistency is expected on the selected days.

General information

Protocol Title: Short course of daily oral ranitidine as a novel treatment for toddler's diarrhea: a double-blind randomized-controlled clinical trial.

Protocol identifying number/date: ISRCTN, ISRCTN10783996/ 8th April 2016

Name and address of sponsor/funder: Self-funded

Name and title of investigators:

1. [name] (Associate Prof). Department of Pediatrics, University of Nigeria Teaching Hospital, Ituku-Ozalla Enugu, Nigeria. [name]. Responsible for application for ethics approval and registration of trial protocol

The illness is currently grouped among the functional gastrointestinal disorders of childhood and has these synonyms namely 'functional diarrhea' and 'irritable colon of childhood' (Rasquin-Weber et al, 1999). Most authors now believe it is a gut motility disorder modulated by dietary factors and excessive fluid intake (Kneepkens & Hoekstra, 1996; Green & Ghisan, 1983; Treem, 1993; Hoekstra, 1998; Dennison, 1996). According to Kneepkens & Hoekstra (1996) and Dennison (1996), low-fat diets and the consumption of fruit juices especially juices high in sorbitol and those with a high fructose: glucose ratio, have been implicated. Thus, dietary modification and reduction of daily fluid intake have been suggested as effective therapeutic measures, and remain the current conventional modality of treatment. Other workers have reported that some probiotics such as *Lactobacillus rhamnosus* and *Saccharomyces boulardii* may also be effective in the resolution of symptoms (Guarino et al, 2009; Roggero et al, 1990).

Interestingly, some researchers have noted that inhibition of gastric secretion with proton-pump inhibitors or H₂-receptor blockers effectively controls the frequent bowel motion and post-prandial urgency associated with functional diarrhea or irritable bowel syndrome, probably by suppressing the gastro-colic reflex (Dave & Rubin, 1999). This finding may open a new vista for the use of these pharmacologic agents in the treatment of toddlers' diarrhea.

Ranitidine (an H₂-receptor antagonist or blocker) is currently licensed in children for the treatment of peptic ulcers. We hypothesize that based on the pharmacologic action of suppressing the gastro-colic reflex, the drug can be a novel treatment for toddlers' diarrhea. Moreover, its safety profile in children makes it an attractive therapeutic option for this disorder.

Although dietary modification and fluid restriction constitute the current standard modality of managing toddlers' diarrhea, strict compliance with dietary measures by caregivers may not be optimal, prompting the desirability of a safe pharmacologic option that can easily be adhered to.

Secondly, despite the benign nature of the disorder, self-advised medications by caregivers and misdiagnosis by physicians in developing countries, where childhood diarrhea remains a major public health problem, may lead to unnecessary laboratory investigations and misapplication of drugs, especially antibiotics. Anecdotal evidence suggests that toddlers' diarrhea is wrongly managed as one of the infective diarrheas by physicians leading to huge treatment costs, and the promotion of antibiotic resistance.

As a novel alternative treatment option, ranitidine given orally for a short duration of 10 days will not only ensure prompt resolution of diarrhea but also ensure better compliance by caregivers. In addition, the treatment cost will be more affordable while the side effects for children at this phase of life are very minimal or non-existent.

Study goals and objectives

Study goal: To establish an alternative therapeutic strategy for toddlers' diarrhea using pharmacotherapy

Primary objective: To determine the effectiveness of a short course of daily oral ranitidine in the treatment of toddlers' diarrhea.

Secondary objective: To compare the effectiveness of oral ranitidine with the probiotic (*Lactobacillus rhamnosus*) in the treatment of toddlers' diarrhea

Study design

A parallel-group randomized controlled trial (RCT)

Methodology

Setting: Pediatric Out-patient Clinic at the University of Nigeria Teaching Hospital (UNTH), Ituku-Ozalla Enugu; and Restoration Medical Centre (Children's Clinic), [name]

Participants' recruitment: Sequential enrolment of 40 participants who met the following eligibility criteria:

(i) Age range of 1-3 years (ii) Duration of diarrhea lasting 3 weeks or more (iii) Historical evidence of the characteristic stooling pattern (iv) Absence of pyrexia and signs of dehydration (v) Normal anthropometry and (vi) Normal findings on stool analysis, microscopy and culture.

Study design: The design is a parallel-group randomized controlled trial (RCT) in which each participant is to be randomly assigned to three groups after meeting the eligibility criteria. For the randomization procedure, we will use permuted-block randomization. The three groups of subjects will consist of a group to be given daily oral ranitidine (3mg/kg) for 10 days (oral ranitidine group-ORG), the group that will receive probiotic for 10 days (PBG) and the control group that will be given a placebo (vitamin C- 50mg daily) for the same duration.

Twenty participants will be assigned to each group- ORG, PBG, and PG. A proforma will be used to record the bio-data, anthropometry of participants, and findings of their stool analysis and stool microscopy/culture.

Intervention: In the ORG- participants will be given oral ranitidine (3mg/kg/day) once daily for 10 days; in the PBG, they will receive probiotics in appropriate doses for 10 days; while in the PG,

the participants will be given vitamin C (50 mg) daily for the same duration. We will ensure allocation concealment by using sequentially numbered, opaque, sealed envelopes (SNOSE) containing the medications. In a double-blind fashion, each enrolled participant will be given color-coded envelopes containing ranitidine, the probiotic, or vitamin C tablets unknown to both the caregivers and outcome assessors.

Follow-up/outcome measures: Stool frequency and consistency will be recorded on days 5 and 10. Any adverse drug reactions will be noted on these follow-up days. There will also be follow-up documentation of stool frequency and consistency 30 days after the end of interventions. Failure of participants to present for documentation of the study outcomes on any of the days will be the qualification for dropping out.

Safety considerations: Follow-up on adverse drug reactions (especially adverse reactions related to ranitidine) will be extended up to 60 days after the end of the intervention. Clinical monitoring of participants for adverse reactions to probiotics will be ensured. Provision will be made for hospitalization and appropriate intervention

Data management and statistical analysis: Data entry and analysis will be done using the Statistical Package for Social Sciences (SPSS) version 25 for Windows. Data will be scrutinized for incorrect information and will be cleaned periodically. The Student's t-test will be used to determine any statistically significant differences in the mean daily stool frequencies of the three intervention groups on the follow-up days. ORG and PBG will be used to report the study effect size. Two standardized measures (Cohen's d and estimation of risk difference) will be used. A 95% confidence interval will be assumed while a p -value < 0.05 will be adopted as the level of statistical significance.

For sample size determination, a predetermined table with the desired statistical power of 0.95 and a Cohen's d (effect size) value of 0.8 will be used, approximating a sample size of 42 (To give room for attrition, 40 will be the final sample size). The value of 0.8 will be chosen to correspond to a large effect size in the predetermined table, indicating the likelihood of a stronger effect.

Study expected outcomes: Normalization of stool frequency and consistency will be the expected outcome of the intervention with oral ranitidine. If no adverse reactions are recorded during and after the study, the intervention may become a paradigm shift in the treatment of toddlers' diarrhea. Clinicians may be more inclined to use this novel pharmacologic approach than the conventional non-pharmacologic methods.

Publication policy/target: We aim to disseminate the findings by publishing them in a reputable international journal within a year of completing the study. [name] will take the lead in the publication. All the investigators will be co-authors.

Duration of research: A proposed period of three years will be allocated for the project implementation and publication of findings. The proposed details include monthly enrollment of eligible participants for 6 months, allocation of participants to intervention groups within a month, follow-up of participants and weekly documentation of outcomes for 6 months, and data analysis for 12 months/manuscript drafting for publication for another 12 months.

Anticipated problems: Seamless participants' enrollment may be affected in the government-run tertiary hospital setting chosen as the study site because of clientele attendance and administrative

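### Two recruiting clinics are named, but the randomisation makes no provision for blocks or envelope series within each clinic

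*Protocol*

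**What the plan says.** Under Methodology, the Protocol gives two places of recruitment: "Setting: Pediatric Out-patient Clinic at the University of Nigeria Teaching Hospital (UNTH), Ituku-Ozalla Enugu; and Restoration Medical Centre (Children's Clinic". Under Anticipated problems it describes the first of these as the "government-run tertiary hospital setting chosen as the study site" and expects enrolment there to be affected by local circumstances.

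Under Study design, "each participant is to be randomly assigned to three groups after meeting the eligibility criteria", followed by "For the randomization procedure, we will use permuted-block randomization". Under Intervention, concealment rests on "sequentially numbered, opaque, sealed envelopes (SNOSE) containing the medications". In the text available, neither section mentions clinic, block size, the number of lists, or how envelopes are to be divided between the two places.

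Under Data management and statistical analysis, mean daily stool frequency is compared between groups by Student's t-test, which has no term for clinic.

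**The concern.** Permuted blocks balance the arms along the list to which they are applied. If both clinics draw on one list, the balance holds for the pooled sequence and need not hold within either clinic.

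There is also a practical difficulty. The envelopes contain the medication, so each must be physically present where the child is treated. One numbered series cannot readily be opened in order at two places. If it is divided between the clinics without regard to blocks, blocks are cut. If both clinics draw from it as children arrive, numbers are likely to be used out of order, which weakens the sequence and the check on concealment that numbering provides.

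With only 13 to 20 children per arm, chance differences between arms in clinic mix can be visible in a baseline table. If stool frequency also differs between clinics, the unadjusted comparison carries avoidable noise. This has to be settled before envelopes are packed; an analysis plan written later can adjust for clinic but cannot restore balance within it.

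**Working it through.** The Protocol gives no figure on clinic balance, so there is none to reproduce.

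**Inputs from the Protocol.** Three arms. Total size is given both as 40 children and as 20 in each of three arms (3 × 20 = 60), so both totals are used; 40/3 gives 13 or 14 per arm. The design effect is d = 0.8.

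**Assumptions, because the Protocol gives no values.** Share of children from the larger clinic 50%, 70% or 80%; block size 3 or 6; a difference between clinics of 0.5 SD in stool frequency, for illustration only.

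**Step 1: closed form.** For two arms of n children with a share p from one clinic, treated as independent binomials, the SD of the difference in shares is √(2p(1−p)/n). At p = 0.5:
- n = 13: √(0.5/13) = 0.196; exact binomial probability of a gap of 20 points or more, 0.327.
- n = 20: √(0.5/20) = 0.158; exact binomial probability, 0.268.

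**Step 2: simulation with three-arm permuted blocks.** The gap is between two given arms in the share from one clinic. A gap of exactly 20 points (4 children of 20) counts as reaching the threshold. Ranges cover the two block sizes and repeated runs.

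| Total | Clinic split | Shared list: mean gap (points) | Shared list: chance of ≥ 20 points | List per clinic: chance of ≥ 20 points |
|---|---|---|---|---|
| 40 | 50:50 | 15–16 | 28–29% | about 0% |
| 40 | 70:30 | 14 | 26–27% | about 0% |
| 40 | 80:20 | 12 | 21–22% | about 0% |
| 60 | 50:50 | 13 | 27% | about 0% |
| 60 | 70:30 | 11–12 | 22–23% | about 0% |
| 60 | 80:20 | 10 | 16–17% | about 0% |

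With a list per clinic the mean gap falls to 2–4 points. At splits of 50:50 and 70:30, the largest minus the smallest arm count within a clinic averages about 3 to 4 children with a shared list (95th percentile 6 to 7). With a list per clinic it averages under 1 (95th percentile 1 to 2).

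**Step 3: effect on the estimate.** Shift = gap × clinic difference.
- A 20-point gap: 0.20 × 0.5 SD = 0.10 SD.
- The mean gap at 50:50: 0.13 to 0.16 × 0.5 SD = 0.06 to 0.08 SD.

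The standard error of a difference in means, in SD units, is √(2/n): √(2/13) = 0.39 and √(2/20) = 0.32. The 0.10 SD shift is therefore 0.10/0.39 = 0.26 to 0.10/0.32 = 0.31 of one standard error.

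**Step 4: loss of precision.** Leaving clinic out adds p(1−p) × 0.5² to a within-clinic variance of 1. At 50:50 this is 0.25 × 0.25 = 0.0625, about 6%, so the standard error rises by a factor of √1.0625 = 1.03. At 80:20 it is 0.16 × 0.25 = 0.04, or 4%.

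**The case against.** The strongest reply is that the Protocol fixes nothing wrong. It never says that there is one list or that the list is unstratified, and a list per clinic would be consistent with its wording. Envelopes could be sent out in whole blocks, which would keep balance at each clinic. The timetable under Duration of research shows allocation within a month as an item separate from six months of enrolment, which is compatible with central allocation. Anticipated problems speaks of the hospital as the study site in the singular, so the second clinic may contribute few children. The same eligibility criteria apply at both places, and nothing shows that their children differ. Unstratified blocked randomisation is valid, and covariates are commonly left to an analysis plan.

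Much of this stands. A reader might infer that one unstratified series is planned; that would be a reading of silence. A reader might infer that the two clinics' children differ; only the clinic types suggest it, and the 0.5 SD used here is an assumption. A reader might also infer that unequal clinic mix would bias or confound the comparison. It would not: under proper randomisation a chance imbalance is part of the random error that the standard error already covers, so the type I error of the t-test is not inflated by it. Nor is a large gap the likely outcome: a gap of 20 points or more between two given arms occurs in fewer than a third of trials.

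What the reply does not remove is the mismatch. Two clinics are named and the mechanism uses physical, numbered medication envelopes, yet no provision links the two. How lists and envelopes are made up and distributed is trial conduct and has to be fixed before packing. A better arrangement is available at almost no cost.

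**Conclusion.** The point holds as a cheap improvement to the design, not as an error in it. The Protocol does not provide for blocks or envelope series within each of its two clinics. If a single series were shared, a gap of 20 points or more in clinic mix between two given arms would occur in roughly 16–29% of trials, against about 0% with blocks by clinic. The range rests on assumed splits of 50:50 to 80:20, blocks of 3 or 6, and totals of 40 to 60.

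The consequence is modest: less balance within clinics and, if clinics differed by 0.5 SD, up to about 6% more variance. A 20-point gap would then move the realised estimate by about a quarter to a third of one standard error, which is small beside the design effect of 0.8 SD. If the clinics do not differ in outcome, the precision argument falls away; orderly use of numbered envelopes at two places remains.

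**What to change.** In the Study design and Intervention text, state that a separate permuted-block list and a separately numbered envelope series will be prepared for each clinic, and that each series will be used strictly in order at its own clinic. Analyse the group comparison with clinic as a factor, so that the analysis matches the randomisation and recovers the precision.

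The cost is a second list before the start, at most one incomplete block per clinic, and one degree of freedom in the analysis. An incomplete block leaves arms within a clinic unequal by at most one child with blocks of 3, or two with blocks of 6. If all children in the end come from one clinic, nothing is lost beyond the unused list.

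### The protocol states two incompatible sample sizes, 40 children in total and 20 in each of three groups (60), and neither gives the stated power of 0.95

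*Protocol*

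**What the plan says.** The total is given as 40 in three places of the protocol:

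- Project Summary, Populations: "40 participants who met the following eligibility criteria".
- Methodology, Participants' recruitment: "Sequential enrolment of 40 participants who met the following eligibility criteria".
- Data management and statistical analysis: "40 will be the final sample size".

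The study design paragraph under Methodology has three arms, ranitidine (ORG), probiotic (PBG) and placebo (PG). It says that "each participant is to be randomly assigned to three groups after meeting the eligibility criteria", and then fixes the arm size: "Twenty participants will be assigned to each group- ORG, PBG, and PG".

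The sample-size paragraph bases the number on "a predetermined table with the desired statistical power of 0.95 and a Cohen's d (effect size) value of 0.8", "approximating a sample size of 42 (To give room for attrition, 40 will be the final sample size". For significance, "p -value < 0.05 will be adopted as the level of statistical significance". It does not say whether the test is one- or two-sided, whether 42 is per group or in total, or what dropout rate is expected.

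**The concern.** Three arms of 20 make 60, and a trial of 40 cannot supply them. Both numbers stand in complete sentences of the current text, so this is not an effect of text extraction or redaction. A separate SAP would not remove it, because the protocol itself fixes both.

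Three things depend on the answer. The first is the length of the permuted-block list and the number of sealed envelopes to prepare. The second is the precision and power of every comparison between two arms. The third is whether a later reader can tell if the trial reached its planned size. The conflict also affects the power statement: the protocol claims 0.95, and the reader needs to know which of the two sizes is meant to deliver it.

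**Working it through.** **Inputs.** Total 40 (Project Summary, recruitment paragraph, sample-size paragraph). Three groups of 20 (study design paragraph). Cohen's d = 0.8, power 0.95 and alpha 0.05 (sample-size paragraph). Student's t-test (same section). Assumed here, because the protocol does not say: two-sided test, no multiplicity adjustment, no dropout.

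**1. The two totals.** 3 × 20 = 60 against 40, a gap of 20 children, or 20/40 = 50% above the stated total. A total of 40 spread as evenly as possible over three arms is 14/13/13.

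**2. Reproducing the protocol's 42.** The normal approximation for two groups is n per group = 2 × (1.960 + 1.645)² / 0.8² = 40.6, so 41. The exact t-test solution is 41.6, so 42 per group, with power 0.952 at 42. The protocol's figure therefore reproduces as the size of each group in a two-group, two-sided comparison. It does not reproduce as a total: 42 children split 21 v 21 give power 0.72. A one-sided test would need 35 per group, so it does not yield 42 either. The stated power needs 2 × 42 = 84 children for the two arms compared, or 3 × 42 = 126 for three equal arms, before attrition.

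**3. Power and precision under each size.** The standard error of a mean difference in SD units is √(1/n₁ + 1/n₂). The noncentrality is 0.8 divided by it. The 95% half-width is t(0.975, n₁ + n₂ − 2) times it.

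| Arms compared | SE (SD units) | Noncentrality | Power, two-sided | 95% half-width |
|---|---|---|---|---|
| 13 v 13 (total 40) | 0.392 | 2.04 | 0.50 | 2.064 × 0.392 = 0.81 SD |
| 14 v 13 (total 40) | 0.385 | 2.08 | 0.51 | 2.060 × 0.385 = 0.79 SD |
| 20 v 20 (total 60) | 0.316 | 2.53 | 0.69 | 2.024 × 0.316 = 0.64 SD |
| 42 v 42 (as the power claim requires) | 0.218 | 3.67 | 0.95 | not needed here |

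**4. Sensitivity to sidedness.** With a one-sided 5% test, power is 0.63 at 13 v 13 and 0.80 at 20 v 20. The gap between the two sizes remains, and neither reaches 0.95.

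**The case against.** **The arm size is explicit.** The study design paragraph, read alone, fixes any two-arm comparison at 20 v 20. The sample-size section names ORG and PBG for reporting the effect size, and 2 × 20 = 40. This makes 20 per arm the likelier intention. It does not resolve the conflict, because the summary and the study design paragraph randomise every enrolled child among three groups, and the recruitment paragraph enrols 40. One may suspect that 40 was set for two arms and not updated for a third, but the documents do not say so.

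**Could 40 mean 40 per group?** That would come close to the stated power (0.94), but it contradicts both twenty per group and enrolment of 40 participants.

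**Optional stopping.** A reader might infer that two written totals let the team look at the data at 40 and then decide whether to go on to 60. The documents do not support this. No interim look is planned. The timetable under Duration of research lists six months of enrolment, then allocation, then follow-up, with analysis last. Caregivers and outcome assessors are blinded. The conflict is an ambiguity about size, not evidence of an uncontrolled stopping rule.

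**Divisibility.** A reader might also treat the fact that 40 is not a multiple of three as a fault in itself. It is not: 14/13/13 is an ordinary result of block randomisation, and the protocol gives no block size that would conflict with it.

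**Settling the number is not enough.** It can fairly be said that choosing 40 or 60 leaves the sample-size paragraph wrong, since neither total gives 0.95. This stands, and the correction has to include the power statement.

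**Conclusion.** The contradiction is real and must be corrected: 40 in three places against 60 implied by the arm sizes, with nothing to reconcile them. Moving from 60 to 40 lowers two-sided power at d = 0.8 from 0.69 to about 0.50–0.51. It widens the confidence interval for a mean difference by about a quarter (0.81/0.64 = 1.27 at 13 v 13). Neither size delivers the 0.95 that the protocol states, because 42 is a per-group requirement.

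The arithmetic of 60 against 40 needs no assumption. The power and interval figures assume a two-sided 5% t-test, near-equal arms, no multiplicity adjustment and no dropout. The protocol counts a missed documentation visit as dropping out, so achieved power would be lower under either size.

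**What to change.** 1. State one total and its arm sizes identically in the Project Summary, the recruitment paragraph, the study design paragraph and the sample-size paragraph. Either write 60 with 20 per group, which keeps the only per-arm figure the protocol gives, or write 40 with 14/13/13 and delete the statement of twenty per group.
2. Fit the randomisation list and the set of envelopes to that total.
3. In the sample-size paragraph, replace 0.95 with the power that the chosen size gives at d = 0.8: about 0.69 for 20 per group, or 0.50–0.51 for 13–14 per group, before dropout. Say that the test is two-sided if it is, and that 42 was a per-group figure. The step from 42 down to 40 cannot be described as room for attrition, since allowing for attrition raises the number to enrol.

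**Cost.** This is a wording amendment and a matching envelope list. The stated power becomes less favourable under either choice. Choosing 60 means 20 more children than the stated total of 40. Choosing 40 adds no recruitment but leaves roughly even odds of detecting the effect the protocol itself names, so it should not be treated as the free option. The documents do not show whether enrolment has begun. If it has, the amendment should be dated and should say how many children had been randomised when the total was settled.

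### The protocol does not state that stool frequency and consistency are recorded before treatment, and its unadjusted t-test, though valid, gives up precision in small arms

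*Protocol*

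**What the plan says.** Four parts of the protocol bear on this.

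- **Enrolment record** (Methodology, Study design): "A proforma will be used to record the bio-data, anthropometry of participants, and findings of their stool analysis and stool microscopy/culture".
- **Outcome schedule** (Follow-up/outcome measures): "Stool frequency and consistency will be recorded on days 5 and 10", and then "There will also be follow-up documentation of stool frequency and consistency 30 days after the end of interventions". The Project Summary gives the same days.
- **Stooling before treatment** (Participants' recruitment): the child must have had diarrhoea for at least 3 weeks, with "Historical evidence of the characteristic stooling pattern". This is a criterion to be met. No count is specified.
- **Analysis** (Data management and statistical analysis): "The Student's t-test will be used to determine any statistically significant differences in the mean daily stool frequencies" among the three groups on the follow-up days. Cohen's d and a risk difference are to be reported. No baseline value, change score or covariate is mentioned.

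The arms hold 20 children each according to Study design, or about 13 each if the enrolment total of 40 in the Project Summary and Participants' recruitment is spread over three groups.

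**The concern.** Every stool measurement that the protocol names falls after treatment has started. If the enrolment form holds only what is listed, three things are lost:

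- The part of the outcome's variance that a child's starting frequency would explain stays in the error term. With 13 to 20 children per arm, that is precision the trial can ill afford.
- The report cannot show that the arms were alike at entry on the variable being compared.
- The report cannot say by how much an individual child's stooling changed.

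The adjustment itself could be left to a statistical analysis plan. Collecting the baseline value could not: a later plan cannot adjust for something nobody wrote down, and a count recalled weeks afterwards is a poor replacement.

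**Working it through.** **Inputs from the protocol.** Planning target: "desired statistical power of 0.95 and a Cohen's d (effect size) value of 0.8 will be used". Significance is at p < 0.05; sidedness is not stated, and two-sided is assumed, in line with the 95% confidence interval. The table figure is 42, with 40 as the final number. Arm size is 20, or 40/3 ≈ 13.

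**Assumption.** The correlation ρ between day-0 and follow-up stool frequency is not in the protocol. It is shown at 0.3, 0.5 and 0.7.

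**Step 1: reproduce the plan's figure.** For a two-sided two-sample t-test with d = 0.8 and power 0.95, the required size is 41.6, so 42 per arm (normal approximation: 41). One-sided testing gives 34 to 35. The 42 is therefore a per-arm figure for an unadjusted comparison, and the plan counts on no gain from a baseline.

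**Step 2: power of the t-test as planned.** At d = 0.8 it is 0.69 with 20 per arm and 0.50 with 13 per arm.

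**Step 3: power with baseline adjustment.** ANCOVA reduces the residual SD by the factor √(1 − ρ²), so the effective standardised difference is 0.8/√(1 − ρ²).

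| ρ | √(1 − ρ²) | Variance removed (ρ²) | Power, 20 per arm | Power, 13 per arm | n per arm for 0.95 |
|---|---|---|---|---|---|
| none | 1.000 | 0% | 0.69 | 0.50 | 42 |
| 0.3 | 0.954 | 9% | 0.73 | 0.54 | 38 |
| 0.5 | 0.866 | 25% | 0.81 | 0.62 | 32 |
| 0.7 | 0.714 | 49% | 0.93 | 0.78 | 22 |

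This formula ignores the degree of freedom spent on the covariate. A simulation of the three-arm ANCOVA (40,000 trials per cell, normal data, only the ranitidine arm shifted, ranitidine against placebo) agreed with each adjusted power to within 0.005.

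**Step 4: would a change score do instead?** Its SD is √(2(1 − ρ)) in units of the outcome SD. At 20 per arm its power is 0.55 at ρ = 0.3, 0.69 at ρ = 0.5 and 0.89 at ρ = 0.7. It loses power at 0.3 and gains nothing at 0.5, so ANCOVA is the better use of the baseline.

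**Step 5: how far chance imbalance carries over.** The 95% range for a chance difference in baseline means is ±1.96 × √(2/n) SD: ±0.62 at 20 per arm and ±0.77 at 13. Only the fraction ρ reaches the outcome. One standard error of what carries over is ρ√(2/n):

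- 20 per arm: 0.09 SD at ρ = 0.3, 0.16 SD at ρ = 0.5
- 13 per arm: 0.12 SD at ρ = 0.3, 0.20 SD at ρ = 0.5

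The effect sought is 0.8 SD, and the t-test's standard error already includes this variation.

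**The case against.** **Silence is not proof of non-collection.** The enrolment list is not worded as complete; it omits the duration of diarrhoea too, which is an eligibility item. A day-0 value would not be expected under a follow-up heading, and a stooling history has to be taken to judge eligibility. Some pages are also not available for review. This stands. A reader might infer that no baseline count is taken, but all that can be said is that the protocol does not state that one is.

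**The t-test is not an error.** This also stands. Under randomisation, the difference in follow-up means is unbiased and the test is valid. A reader might infer that chance differences in starting frequency distort the result directly. Step 5 of the working shows that they pass through only in proportion to ρ and are already in the standard error.

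**Normalisation does not need a day-0 count.** A reader might infer that the expected outcome cannot be shown without one. But normal stooling is a state reached at follow-up. All children enter with diarrhoea of at least 3 weeks, and the arms can be compared by means or by the planned risk difference. What is missing is the size of change within a child.

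**The benefit depends on an unsourced correlation.** Nothing in the protocol shows that starting frequency is the strongest predictor of the outcome. Selecting every child for diarrhoea, and relying on caregiver recall, could both lower ρ. At 0.3 the gain is about four percentage points of power. This limits the size of the point but does not remove it, since power rises at every value shown.

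**Conclusion.** The point holds as a low-cost improvement, not as a flaw that invalidates the comparison. The protocol names no pre-treatment record of its outcome variable and fixes an unadjusted comparison of follow-up means. At d = 0.8 and two-sided 0.05, the precision given up is the gap between 0.69 and 0.73 to 0.93 in power at 20 per arm, or between 0.50 and 0.54 to 0.78 at 13 per arm, for ρ from 0.3 to 0.7. Those ranges rest on an assumed correlation and on roughly normal outcomes with a common SD. Baseline comparability on the outcome and within-child change also go undocumented, whatever ρ is.

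Adjustment should not be read as rescuing the sample size. Using 42, a per-arm number, as if it were a total, and the conflict between 40 in all and 20 in each of three arms, are separate problems. Even at ρ = 0.7, power of 0.95 needs 22 per arm.

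**What to change.** 1. Add day-0 stool frequency and consistency to the enrolment form, taken before randomisation and asked in the same way as at the follow-up visits. If this is already intended, say so.
2. Replace the t-test on follow-up stool frequency with an ANCOVA of follow-up frequency on arm and day-0 frequency, fitted to all three arms, and report the adjusted differences between arms with 95% confidence intervals. Do not use an unadjusted change score.

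The cost is two fields at a visit that already takes a stooling history, and one sentence in the analysis section. If the correlation proves low, little is gained, but little has been spent. The collection step has to be in place before the first child is randomised. The sample-size passages must be reconciled separately.
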